5.7.3. COVID-19-like Signs and Symptoms

Procedures to be performed in the event a participant experiences signs or symptoms suggesting possible COVID-19 are detailed in CTP Sections 1.3 Schedule of Activities and 8.1.2 Procedures in case of COVID-19-like Signs and Symptoms.

The presence of SARS-CoV-2 infection will be assessed at the study site by molecular testing using the nasal swab sample.

The following analyses will use the FAS set and will be conducted at the time of the final analysis:

The number and percentage of participants with at least one molecularly confirmed SARS-CoV-2 infection will be tabulated by vaccine regimen, for the entire study period only.

The number and percentage of participants with at least one positive non-S protein ELISA (e.g., N ELISA), if available, will be tabulated by vaccine regimen. The analysis will be repeated pooling all active regimens vs. placebo, where data from all cohorts will be pooled.

For each participant with confirmed COVID-19 infection, a narrative will be prepared based on the visit performed 28 days after the onset of COVID-19 signs and symptoms and other selected information from the clinical database, as available:

- participant ID
- vaccination regimen
- sex, race, ethnicity, age, BMI, dates at which vaccinations were received
- pulse oximetry
- physical examination findings based on the visit performed 28 days after the onset of COVID-19 signs and symptoms
- vital signs including body temperature based on the visit performed 28 days after the onset of COVID-19 signs and symptoms
- Humoral immune responses as collected at the planned time points + those obtained from the blood sample taken on the visits performed 3 and 28 days after the onset of COVID-19 signs and symptoms. This information may be presented graphically.

For the analysis of the SIC (Patient Reported Outcomes, PRO) data, the following considerations apply

- An “episode” is defined as a period in which any symptoms are reported on the SIC, starting from the first day on which symptoms were reported until the first day that the PRO was not completed because the symptoms had resolved (this will be indicated in the

SDTM data, with reason for not completing the PRO = “Symptoms resolved” (or similar) or death

- A symptom (e.g. feeling generally unwell, fatigue, physical weakness, cough, etc.) is assumed to be present on each day the associated Yes/No question is answered “Yes” or the associated severity question has a rating > 0.
- If the PRO was not completed due to the participant being too ill or due to the participant being hospitalized, the symptom; will be considered present with severity score 10. If the PRO was completed due to any other reason, no imputations will be done.

Duration of the episode will be calculated as episode end date – episode start date. Duration of each symptom will be calculated as last day of symptom reporting – first day of symptom reporting + 1. Duration of the maximum severity is defined as the last day of reporting the maximum severity – the first day of reporting the maximum severity + 1.

The following analyses will be conducted for confirmed SARS-CoV-2 infection cases:

- At the level of first episodes, the following statistics will be calculated: number of episodes, mean and median duration of episodes (with min, max, q1 and q3), and mean and median number of symptoms reported per episode (with min, max, q1 and q3).
- At the level of the symptoms for each first episode, the following statistics will be calculated: number of participants experiencing the symptom, mean and median duration of each symptom (with min, max, q1 and q3), median (with q1 and q3) of maximum severity of each symptom, median duration of the maximum severity of each symptom (with min, max, q1 and q3).
- At the level of the participants, for each episode and each symptom separately, the duration, and minimum and maximum severity scores will be tabulated (as available).

In addition, participant listings will be provided containing the SIC information for each time point.

More details about these analyses will be provided in the DPS.

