400 participants (75 participants per active vaccine group, 25 in the placebo group) will be randomized in parallel in a 3:3:3:3:3:1 ratio to 1 of 6 vaccination groups. Participants will receive a 2-dose (56-day interval, Groups 1-3) vaccination regimen at different dose levels $(5 \times 10^{10} \text{ vp}, 2.5 \times 10^{10} \text{ vp}, \text{ and } 1.25 \times 10^{10} \text{ vp})$ or single-dose vaccination regimen (Groups 4-5) at different dose levels $(1 \times 10^{11} \text{ vp}, 5 \times 10^{10} \text{ vp})$, or placebo (Group 6). For blinding purposes, participants in the single-dose groups (Groups 4-5) will receive a placebo vaccination on Day 57. Additional exploratory cellular immunogenicity evaluations (PBMC) will be performed in a subset of participants (21/group in Groups 1-5, 7 in Group 6; at selected sites). Participants in Group 6 who received 2-doses of placebo in the primary vaccine regimen will receive 2 doses of active vaccine at a single dose level of $5 \times 10^{10} \text{ vp}$, at a 28-day interval.

Groups 7-8

75 participants (50 participants in the active vaccine group, 25 in the placebo group) will be randomized in parallel in a 2:1 ratio, to 1 of 2 vaccination groups. Participants will receive a 2 dose (28-day interval, Groups 7) vaccination regimen at a 5×10^{10} vp dose level or placebo (Group 8). Participants in Group 8 who received 2-doses of placebo in the primary vaccine regimen will receive 2 doses of active vaccine at a single dose level of 5×10^{10} vp, at a 28-day interval.

Groups 9-10

75 participants (50 participants in the active vaccine group, 25 in the placebo group) will be randomized in parallel in a 2:1 ratio, to 1 of 2 vaccination groups. Participants will receive a 2 dose (84-day interval, Group 9) vaccination regimen at a 5×10^{10} vp dose level or placebo (Group 10). Participants in Group 10 who received 2-doses of placebo in the primary vaccine regimen will receive 2 doses of active vaccine at a single dose level of 5×10^{10} vp, at a 28-day interval.

Vaccination Schedule – Adults

Adults ≥18 to ≤55 Years and ≥65 Years

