The first doses of Ad26.COV2.S study vaccine at 2.5x10¹⁰ vp were to be administered to a sentinel group of 11 participants in Groups A-C (randomly assigned at a ratio of 5:5:1 to Ad26.COV2.S, with 5 each from Groups A and B, and 1 participant in Group C to receive placebo), to monitor for any unexpected severe adverse reactions. The sentinel participants were to be vaccinated at least 1 hour apart even if enrolled at different study sites. A telephone call was to be made to each of these 11 sentinel participants on Day 4 post-vaccination to collect safety data, which was to include solicited and unsolicited AEs and SAEs. The collected data were to be reviewed in a blinded manner by the principal investigator and the sponsor's study responsible physician/scientist (SRP/S). Randomization and vaccination of additional participants was to be halted until the review was completed. The SMC was to review the unblinded Day 4 post-vaccination safety data, including solicited and unsolicited AEs and SAEs, and if the safety profile was found to be acceptable, a safety cohort of 22 participants in Groups A-C (randomly assigned at a ratio of 5:5:1 to Ad26.COV2.S, with 10 each from Groups A and B, and 2 participants in Group C to receive placebo) was to be enrolled. The Day 8 post-vaccination safety data from both sentinel groups, including solicited and unsolicited AEs and SAEs, was also to be reviewed by the SMC, and in the absence of any safety concerns, the enrollment and vaccination of the remainder of the participants for Groups A-C (49 participants) in this age group was to proceed, and simultaneously, sentinel enrollment in Groups D-F (to receive Ad26.COV2.S study vaccine at 5x10¹⁰ vp) was to start. In addition, enrollment of the younger age group of adolescents (12-15 years, inclusive) was to proceed for Groups A-C.

After vaccination, all participants were to remain under observation at the study site for at least 1 hour (including participants in the Sentinel and Safety Cohort) to monitor for the presence of any acute reactions and solicited events.

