5.7.2. COVID-19 case monitoring to detect imbalances across study groups (harm monitoring)

An unblinded statistician, who is not otherwise involved in the study, will monitor the number and severity of molecularly confirmed COVID-19 cases in the Ad26COVS2.S and placebo groups to identify an imbalance between groups if it occurs. The unblinded statistician will inform the DRC as soon as an imbalance between groups is detected.

As soon as 3 confirmed COVID-19 cases have occurred, and with every additional case, the unblinded statistician will tabulate the cases according to whether the participant received Ad26.COV2.S or placebo (i.e. active regimens will be pooled) and calculate the difference in proportions between the two groups (proportion in active – proportion in placebo). Two (two-sided) confidence intervals around this difference will be constructed, a 95% CI and an 80% CI (i.e. using z-values corresponding to alpha = 0.05 and alpha = 0.20), using Newcombe’s method without continuity correction.

The Newcombe’s confidence interval for a difference between proportions is calculated as follows:

$$\begin{aligned} \text{Lower limit: } & (\hat{p}_1 - \hat{p}_2) - \sqrt{(\hat{p}_1 - L_1)^2 + (U_2 - \hat{p}_2)^2} \\ \text{Upper limit: } & (\hat{p}_1 - \hat{p}_2) + \sqrt{(U_1 - \hat{p}_1)^2 + (\hat{p}_2 - L_2)^2} \end{aligned}$$

Where L_i and U_i are the Wilson Lower and Upper confidence limits for p_i . The Wilson confidence limits without continuity correction for each binomial proportion $p_i = x_i/n_i$ ($i=1,2$) is given by:

$$\frac{1}{2(n_i + z^2)} \left((2n_i \hat{p}_i + z^2) \pm z \sqrt{4n_i \hat{p}_i (1 - \hat{p}_i) + z^2} \right)$$

If the upper limit of the one-sided 95% CI around the difference in proportions exceeds 0.10 (i.e. >10 percentage points difference between active and placebo), and the lower limit of the one-sided 80% CI around the difference in proportions exceeds 0 (i.e. >0 percentage points difference between active and placebo), then the unblinded statistician will conclude that there is an imbalance between active and placebo (where the proportion in active is greater than the proportion in placebo). Otherwise, the statistician will not conclude that there is an imbalance.

The same operations will be executed for severe COVID-19 cases, using these definitions of “severe” cases:

- COVID-19 cases requiring hospitalization,
- COVID-19 cases requiring hospitalization and the patient being admitted to the Intensive Care Unit,

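### The pooled active-versus-placebo N-ELISA table in SAP 5.7.3 is unstratified although allocation ratios differ widely between group sets; a by-set display and stratified estimate would remove a foreseeable, probably small, distortion

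*SAP*

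**What the plan says.** SAP 5.7.3, on the FAS and at the final analysis, counts participants positive on a non-S protein ELISA for each vaccine regimen, provided the assay exists. It then adds: "The analysis will be repeated pooling all active regimens vs. placebo, where data from all cohorts will be pooled". No stratification, weighting or adjustment by group set is mentioned. SAP 5.1.5 makes within-group analysis the default unless pooling is stated, so the pooling here is deliberate.

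The Protocol Synopsis sets the allocation:

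- Groups 1-6: five active groups of 75 and one placebo group of 25, in the ratio 3:3:3:3:3:1.
- Groups 7-8, with Groups 9-10 described in the same words: "75 participants (50 participants in the active vaccine group, 25 in the placebo group) will be randomized in parallel in a 2:1 ratio".
- Adolescent sentinels, 11 in number: "randomly assigned at a ratio of 5:5:1", which is 5 in Group A, 5 in Group B and 1 on placebo in Group C.
- Adolescent safety cohort, 22 in number: "with 10 each from Groups A and B, and 2 participants in Group C to receive placebo".

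SAP 5.7.2 (harm monitoring) also contrasts Ad26.COV2.S with placebo after pooling: "active regimens will be pooled". SAP Appendix 2 merges Groups 7-8, apart from two participants, with Groups 1 and 6 in the FAS for safety analyses.

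**The concern.** The two pooled columns are built from the group sets in very different proportions. If the sets differ in infection risk, for example through calendar time, site or exposure, that difference enters the active-placebo contrast even when the vaccine does nothing. It could look like benefit or harm, or mask a real effect. It is also systematic, so an interval around the crude difference would not reveal it.

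The by-regimen table is only a partial safeguard. Footnotes in SAP 5.6 and 5.7.1 describe table columns by planned regimen, with a single placebo-placebo column as the example, so Groups 6, 8 and 10 may appear together. If the Appendix 2 merging is carried over to this FAS table, Groups 7-8 would not be visible as a set.

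**Working it through.** **1. Reproduce the planned numbers.** 400 split 3:3:3:3:3:1 gives 5 × 75 + 25. 75 split 2:1 gives 50 + 25, twice. 33 split 5:5:1 gives 15 + 15 + 3. Adults: 400 + 75 + 75 = 550. Adult placebo: 25 + 25 + 25 = 75. Adolescents: 33. All three totals match the Synopsis. (Protocol 4.1 prints 3:3:3:3:1 for the six groups; only the Synopsis ratio yields 75 per active group.)

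**2. Composition of the pooled columns.**

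| Set | Active | Placebo | Ratio | % of 505 active | % of 78 placebo |
|---|---|---|---|---|---|
| Groups 1-6 | 375 | 25 | 15:1 | 74.3 | 32.1 |
| Groups 7-8 | 50 | 25 | 2:1 | 9.9 | 32.1 |
| Groups 9-10 | 50 | 25 | 2:1 | 9.9 | 32.1 |
| A-C | 30 | 3 | 10:1 | 5.9 | 3.8 |

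Groups 7-10 together: 100/505 = 19.8% of active, 50/78 = 64.1% of placebo.

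**3. Size of the artefact with no vaccine effect.** Let r1, r2, r3 be the risks in Groups 1-6, Groups 7-10 and A-C. Crude active minus placebo is

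(375/505 − 25/78)·r1 + (100/505 − 50/78)·r2 + (30/505 − 3/78)·r3 = 0.422·r1 − 0.443·r2 + 0.021·r3.

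With r3 = r1 this is 0.443·(r1 − r2), or about 0.44 points per 1-point gap. The documents give no infection rates, so every risk below is an assumption. The half-width is 1.96 × √[pA(1−pA)/505 + pP(1−pP)/78].

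| r1, r2, r3 (%) | Crude active % | Crude placebo % | Difference (points) | RR | 95% half-width (points) |
|---|---|---|---|---|---|
| 2, 4, 2 | 2.40 | 3.28 | −0.89 | 0.73 | 4.2 |
| 2, 6, 2 | 2.79 | 4.56 | −1.77 | 0.61 | 4.8 |
| 5, 10, 5 | 5.99 | 8.21 | −2.22 | 0.73 | 6.4 |
| 10, 5, 5 | 8.71 | 6.60 | +2.11 | 1.32 | 6.0 |
| 6, 2, 2 | 4.97 | 3.28 | +1.69 | 1.51 | 4.4 |
| 5, 5, 15 | 5.59 | 5.38 | +0.21 | 1.04 | 5.4 |

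With A-C at 10% in the fourth row, the difference is 0.443 × 5 = +2.2. On adults only (475 v 75), the 5% v 10% case gives −2.28, so leaving out the adolescents changes little. In the 5, 10, 5 case, 2.2 points is about 1.7 events among 78 placebo recipients.

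**4. Sampling day alone.** Protocol 8.1.3 ties adult N-ELISA samples to antigen presentation and Vaccination 2. I took Days 197, 169 and 225 for the three adult sets (28 days after antigen presentation) and assumed Day 337 for adolescents. At the same constant hazard in every set, risk = 1 − exp(−λ·days), with λ = −ln(1 − annual risk)/365. Annual risks of 5%, 10% and 20% give artefacts of 0.04, 0.08 and 0.16 points.

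**5. What stratification does.** The Mantel-Haenszel RR is Σ(xᵢ·pᵢ/nᵢ) / Σ(yᵢ·aᵢ/nᵢ), with aᵢ active and pᵢ placebo participants, nᵢ = aᵢ + pᵢ, and xᵢ, yᵢ the active and placebo cases. On expected counts it returns the within-set RR exactly.

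| True RR | Crude RR (5, 10, 5) | Crude RR (10, 5, 5) | Stratified RR |
|---|---|---|---|
| 0.70 | 0.51 | 0.92 | 0.70 |
| 1.00 | 0.73 | 1.32 | 1.00 |
| 1.30 | 0.95 | 1.72 | 1.30 |

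**6. Price in precision.** At a common risk, the variance factor is 1/505 + 1/78 = 0.01480 for the crude difference. For the Mantel-Haenszel difference it is 1/Σ(aᵢpᵢ/nᵢ) = 1/(23.44 + 16.67 + 16.67 + 2.73) = 0.01681. √(0.01681/0.01480) = 1.07, an interval about 7% wider.

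**The case against.** The strongest case against is that little in the documents suggests a material distortion.

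- The table reports numbers and percentages for an exploratory endpoint, if the assay is available. SAP 5.7.3 plans no test or interval for it, and Protocol 9.1 rules out formal hypothesis testing. This stands and limits the severity.
- A reader might infer that the pooled table is the only planned view of serological infection by arm. It is not: the by-regimen table comes first, although it may combine placebo groups and hide Groups 7-8.
- A reader might infer that only within-set contrasts are randomised. Separate adult randomisations are the natural reading of the set-by-set ratios in the Synopsis. However, the Synopsis and Protocol 4.1 also describe adults as assigned to one of ten groups, and Protocol 6.3 names only site and age as adult stratification factors. Under one ten-group schedule, adult baseline risk would balance in expectation.
- A reader might infer that the sets are known to differ in risk. No passage documents a risk gap between Groups 1-6 and 7-10. Differences that are documented do little: sampling day moves the result by under 0.2 points, and the adolescent set by about 0.2 points even at 15% v 5%. Whether adolescents enter the table is itself unclear, since SAP Section 1 promises only limited adolescent outputs. SAP Appendix 2 puts Vaccination 2 in Groups 7-8 at 51 to 72 days for all but two participants, close to the 56-day schedule.
- A reader might infer that the SAP 5.7.2 trigger is compromised. That rule concerns molecularly confirmed cases, and nothing here evaluates its behaviour.

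What survives is that the imbalance in composition is certain from the planned numbers, and guarding against it needs no proof that risks differ.

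**Conclusion.** The point holds as a minor, inexpensive improvement. The pooled columns differ sharply in composition, so any risk gap between Groups 1-6 and 7-10 passes into the crude contrast at about 0.44 points per point. That is roughly 2 points in either direction for an assumed 5% v 10%. In every scenario examined this is smaller than the 95% half-width of about 4 to 6.5 points. The conclusion rests on the planned group sizes, assumed infection risks and, for baseline imbalance between adult sets, the assumption that those sets were randomised separately. The documents do not show that the pooled table will mislead, only that it is open to a bias that stratification removes.

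**What to change.** In SAP 5.7.3, add a table of N-ELISA positivity for active v placebo within each set as randomised (Groups 1-6, 7-8, 9-10, A-C). State that Groups 7-8 stay identifiable in it despite the merging in SAP Appendix 2, and say whether pooling over all cohorts includes the adolescents. If a pooled contrast is reported, give it as a Mantel-Haenszel or stratified Newcombe estimate over these sets. Optionally, show by-set counts beside the pooled difference in SAP 5.7.2, leaving its trigger rule unchanged.

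The cost is a few lines of SAP text, one extra table and a slightly wider interval. The adolescent set, with 3 placebo recipients, will contribute little. No new data are needed.

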- A second nasal swab will be obtained on COVID-19 Day 3-8 following the same procedures as the first nasal swab. The second nasal swab may also be collected at home, at the hospital, or at another location, if needed, by a study site staff, if appropriate procedures are in place. The presence of SARS-CoV-2 infection will be assessed at the study site by molecular testing using the nasal swab samples. The nasal swabs may be tested at the central laboratory for the presence of SARS-CoV-2 and other respiratory pathogens using a broad respiratory pathogens panel. Leftover nasal swab samples will be stored and might be used for central laboratory confirmation and/or quantification of SARS-CoV-2 and for detection of other respiratory pathogens. A physical examination, vital signs measurements and pulse oximetry will be performed and a blood sample for assessment of the humoral immune response and other biomarkers will be taken.
- From COVID-19 Day 3-8 onwards: Additional swabs should be taken by a healthcare professional from the participant as soon as possible, but with a minimum of 1 day between the swabs, until 2 consecutive negative swabs are obtained, ie, twice weekly or more frequently until resolution. These precautionary measures are to ensure that site staff who

²² As several of the prespecified criteria for suspected COVID-19 overlap with vaccine-related reactogenicity, investigators' clinical judgement is required to exclude vaccine-related events.

come into physical contact with a participant deemed to be a COVID-19 case undertake the proper safety procedures such as wearing of personal protective equipment.

- Participants should complete the SIC (see Section 10.7) and record their highest body temperature daily starting on the first day of trigger onset. Blood oxygen saturation and pulse rate should be measured using a pulse oximeter 3 times a day, preferably in the morning, at lunch time, and in the evening.
- Collection of data will continue until resolution of the COVID-19 episode, defined as having 2 consecutive days with no COVID-19-related signs or symptoms and 2 consecutive SARS-CoV-2 negative nasal swabs.

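### SAP 5.7.3: two SIC derivation rules can add symptoms that were never reported and count symptom-free days in episode duration (exploratory endpoint)

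*SAP*

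**What the plan says.** SAP 5.7.3 sets the rules for the SIC, the daily symptom questionnaire in Protocol Appendix 7.

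- **Missed days.** The trigger is a day left blank through severe illness or a hospital stay. On such a day "the symptom; will be considered present with severity score 10". Days missed for different causes get a rule of their own, which as printed says: "If the PRO was completed due to any other reason, no imputations will be done".
- **Episode end.** An episode is described as a period in which symptoms are reported. It runs from the first symptomatic day "until the first day that the PRO was not completed because the symptoms had resolved", or to death.
- **Durations.** The episode formula adds no day: "Duration of the episode will be calculated as episode end date – episode start date". The formula for a single symptom counts both end days: "Duration of each symptom will be calculated as last day of symptom reporting – first day of symptom reporting + 1". The third formula has the same inclusive form, applied to days at the highest score: "Duration of the maximum severity is defined as the last day of reporting the maximum severity", less the earliest such day, with 1 added.
- **Outputs.** For first episodes in confirmed cases: mean and median number of symptoms reported per episode, number of participants with each symptom, symptom durations, and median and quartiles of maximum severity.

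Protocol 8.1.2 continues data collection until the episode resolves, "defined as having 2 consecutive days with no COVID-19-related signs or symptoms and 2 consecutive SARS-CoV-2 negative nasal swabs". In Protocol 1.3.7, note 2 to the table and footnote b say the same for the SIC in swab-positive cases.

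**The concern.** The imputation rule speaks of a single symptom but does not say which. The preceding SAP bullet uses the word generically for any SIC item, so the natural programming is to set every item to present at 10. Skin rash, sneezing and eye discharge would then be tabulated as present in anyone who missed a day through severe illness, whether or not they had them. Two programmers could also reach different tables from the same text.

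The episode rule has a different fault. A completed SIC with no symptoms does not end the episode, so days spent symptom-free while waiting for swabs can be counted as illness. If the diary stops for some other reason, no end date is defined at all.

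At stake is the exploratory endpoint of presence and severity of COVID-19 signs and symptoms. The imputation touches only the sickest participants, whose symptom profile is of most interest.

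**Working it through.** The documents give no figure to reproduce here, so the check applies the SAP rules to an illustrative case.

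**Inputs from the documents.** Appendix 7 has 25 items rated 0 to 10 and 4 yes/no items without a rating (shaking, smell, taste, red or bruised feet or toes), 29 in all. The duration formulas are those quoted above.

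**Assumptions, not from the documents.** Eight true symptoms on days 1 to 10; true maximum severity 6 on days 3 to 6; SIC missed on days 5 to 7 through hospitalisation; a share *f* of cases with at least one such day, from 2% to 50%.

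**1. Imputation read as every item, one participant**

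- Symptom count: 8 becomes 25 (29 if the unrated items are set to present).
- Maximum severity: 10 for all 25 rated items.
- Duration of a symptom never present: 0 becomes 7 − 5 + 1 = 3 days, if imputed days count as reporting days.
- Duration of a symptom present on days 1 to 10: unchanged, 10 days.
- Duration of maximum severity: 6 − 3 + 1 = 4 days becomes 7 − 5 + 1 = 3, or 1 if a single day is missed. This one gets shorter.

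**2. Group mean symptom count** = 8(1 − *f*) + 25*f*

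| *f* | Mean count |
|---|---|
| 0 | 8 |
| 2% | 8.3 |
| 10% | 9.7 |
| 20% | 11.4 |
| 50% | 16.5 |

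**3. Median of maximum severity, 20 cases**

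- Common symptom, true maximum 6 in all 20: the median stays 6 with 1, 2 or 4 imputed cases, is 8 with 10, and is 10 with 11.
- Rare symptom, truly present in 1 of 20 at severity 3: two other imputed cases give 1 + 2 = 3 participants with values 3, 10, 10, so the median is 10.

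**4. Episode duration.** Start on day 1, last symptom on day 10, then *x* symptom-free days with the SIC still completed. The end date is day 10 + *x* + 1, so duration = (10 + *x* + 1) − 1 = 10 + *x*.

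| Symptom-free diary days *x* | SAP duration | Excess over 10 symptomatic days |
|---|---|---|
| 0 | 10 | 0 |
| 2 (protocol minimum) | 12 | 2 |
| 4 | 14 | 4 |
| 7 | 17 | 7 |

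The formula equals the symptomatic days only if the diary stops on the first symptom-free day. Per-symptom duration and duration of maximum severity use first and last reporting days, so a late diary stop does not change them.

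**The case against.** Scoring days missed through severe illness at the worst value is a recognised conservative choice, because such missingness is informative. The SAP never says every item; its wording is singular and garbled. It also counts symptoms that were reported, and does not settle whether an imputed day is a report. Hospitalisation alone triggers nothing: the SIC must be missed for that reason. Protocol 5.2.1 excludes most adults with comorbidities linked to severe COVID-19, so such days may be few. Listings will show the SIC at each time point, each confirmed case gets a narrative, and detail is deferred to the data presentation specifications.

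On episode end, two places in the protocol suggest completion only while symptomatic: the list of study-specific materials in Section 8, and the reminder to participants in 8.1.2. On that reading the excess is 0 days.

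Much of this stands. It limits the size of the problem and makes the diary's stopping point ambiguous. It does not make the rules adequate. A score rule with no stated scope, which cannot apply to 4 of 29 items, needs correcting in the SAP. Protocol 1.3.7 and 8.1.2 do extend SIC collection to resolution in swab-positive cases. Ending the episode on the last symptomatic day is right under either reading.

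A reader might infer that SIC symptom counts, severities and durations are overstated across the board. The documents do not support that. Coverage of all items is an interpretation, only episode duration depends on the episode-end rule, duration of maximum severity can be understated, and no group maximum of severity is planned.

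**Conclusion.** The point holds as a fault in two derivation rules. Read as covering all items, the score-10 rule can put never-reported symptoms into the tables. It raises symptoms per episode (mean 8 to 9.7 if 10% of cases are affected, under the assumptions above) and distorts rows for rarer symptoms, while medians for common symptoms hold until about half of cases are affected. The episode rule adds at least 2 days wherever the SIC is continued to protocol-defined resolution, and none where it stops with the symptoms. The sentence on other reasons says the opposite of what it must mean.

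The actual size is unknown: the documents do not say how many confirmed cases will have such days, nor when participants stop the diary. No hypothesis is tested on this endpoint, so the consequence is misleading descriptive tables and not a wrong trial conclusion.

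**What to change.** In SAP 5.7.3:

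1. Limit the imputation of presence and score 10 to symptoms present on the last completed SIC before the missed day. For the four unrated items, only presence can be imputed.
2. State that an imputed day does not make an unreported symptom count as reported, and give an observed-data summary alongside. Ongoing symptoms still receive a 10, so that summary is needed to show its effect.
3. Define episode end as the last day with any symptom reported (or imputed under item 1), or death, with duration = end − start + 1. In the example this gives 10 − 1 + 1 = 10 days however long the diary is kept.
4. In the rule for other reasons, change *completed* to *not completed*.

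The cost is SAP wording and a small amount of extra derivation; no new data are needed. The downside is that symptoms first arising during missed days may be understated.

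### The SAP's duration of maximum severity counts lower-scored days as days at the maximum whenever the peak score recurs on non-consecutive days

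*SAP*

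**What the plan says.** SAP 5.7.3 gives two durations for individual SIC symptoms, both as a last day minus a first day plus 1.

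- Symptom: "Duration of each symptom will be calculated as last day of symptom reporting", minus the first such day, plus 1.
- Maximum severity: "Duration of the maximum severity is defined as the last day of reporting the maximum severity", minus "the first day of reporting the maximum severity + 1".

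The second feeds the planned "median duration of the maximum severity of each symptom (with min, max, q1 and q3". No mean is planned for it. Duration is also tabulated per participant, episode and symptom.

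The same section sets symptom presence day by day: a symptom "is assumed to be present on each day the associated Yes/No question is answered" yes, or is rated above 0. The protocol asks for daily completion (section 8.1.2): "Participants should complete the SIC (see Section 10.7) and record their highest body temperature daily starting on the first day of trigger onset". Days not completed because the participant was too ill or hospitalized are imputed with a score of 10. For other reasons nothing is imputed. Further detail is left to the Data Presentation Specifications (DPS), which are not among the documents.

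**The concern.** The name of the statistic promises the time a symptom spent at its worst. The formula gives the time between the first and last visits to the worst score. These agree only if the participant stays at that score throughout. Nothing in section 5.7.3 requires the days to be consecutive, subtracts the days between, or provides for a repeated peak.

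The risk is greatest for a mild symptom, where the maximum is a low score that is easily reached twice. A reader of the output would take the figure as days at peak severity, and could conclude that mild symptoms stay at their worst for longer than the diaries show.

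**Working it through.** **Inputs.** The formula and the planned summary statistics are from SAP 5.7.3. Daily scoring from 0 to 10 is from protocol 8.1.2 and Appendix 7. Neither document gives a duration figure to reproduce, nor any data on the course or day-to-day variability of symptoms.

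**Formulas.** Let M be the highest daily score, F the first day and L the last day with score M.

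- SAP rule: span = L − F + 1.
- Day count: number of days with score M.
- Span − count = number of days between F and L without score M. This is never negative, and is zero only when the peak days are consecutive.

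**Worked diaries (complete, no missing days).**

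| Daily scores | F, L | Span | Count |
|---|---|---|---|
| 2, 5, 7, 7, 7, 4, 2, 1 | 3, 5 | 5 − 3 + 1 = 3 | 3 |
| 3, 7, 4, 3, 3, 4, 7, 2 | 2, 7 | 7 − 2 + 1 = 6 | 2 |
| 8, 3, 2, 1, 1, 2, 8 | 1, 7 | 7 − 1 + 1 = 7 | 2 |

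**Illustrative size.** All course shapes below are assumptions, with 20,000 simulated diaries per setting.

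*Moderate to severe symptom:* 14 days, rise and fall, peak 4 to 8.

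| Daily noise SD | Mean span | Mean count | Difference | Share overstated |
|---|---|---|---|---|
| 0 | 1.52 | 1.52 | 0 | 0% |
| 0.5 | 1.78 | 1.69 | 0.09 | 8% |
| 1 | 1.91 | 1.60 | 0.31 | 19% |
| 2 | 1.96 | 1.40 | 0.56 | 21% |

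*Statistics the SAP actually plans:* 18 settings (7, 14 or 21 days; peak 2, 4 or 6; SD 0.7 or 1.2), with a rise to day 3 and then exponential decay with a constant of one third of the episode length.

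- The median was the same by span and by count in 17 of 18 settings. The exception was 3 days against 2 (21 days, peak 2, SD 0.7). Across three decay rates it differed in 6 of 54 settings, by 1 to 2 days.
- The upper quartile moves more. In a similar set of courses with peak about 2 over 14 to 21 days, q3 was 6 to 10 days by span against 2 to 4 by count, and 39% to 51% of records were overstated.
- For a 7-day episode with peak 6, 0% to 2% of records were overstated.

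**The case against.** The strongest reply is that the SAP states its definition openly, the analysis is exploratory and descriptive with no hypothesis test, the planned median barely moves, and the SIC listings at each time point show the daily scores. A day count also has a weakness: days missed for reasons other than illness or hospitalization are not imputed, so a count can lose real days at the maximum that a span would bridge. The DPS might also add a rule. All of this limits the consequence, and the missing-day point must be part of any fix. It does not make the span a measure of time at maximum severity, and the SAP states the formula outright instead of deferring it.

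Stronger readings are tempting but not supported:

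- *Symptom duration is wrong in the same way.* A reader might infer this from the identical formula. First to last report is a legitimate onset-to-last-report measure, close to the SAP's own duration for solicited adverse events (section 5.6.1.2, start to resolution). It needs a clear label only.
- *No other duration is reported.* Episode duration is also planned, with mean, median, range and quartiles.
- *Waiting for negative swabs stretches the span.* Protocol 8.1.2 says "Collection of data will continue until resolution of the COVID-19 episode, defined as having 2 consecutive days with no COVID-19-related signs or symptoms" together with two negative swabs. That governs data collection. The SAP's analysis episode ends on the first day the SIC was not completed because symptoms had resolved (or at death), and the symptom statistics use first episodes.
- *Durations are broadly inflated.* Means from assumed courses can suggest this, but no mean is planned for this statistic, and the median is usually unchanged.

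**Conclusion.** The point holds in a limited form. For maximum severity, the stated formula does not give the quantity it names when the peak score recurs on non-consecutive days. This follows by arithmetic and needs no assumption. With consecutive peak days there is no error.

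The size in this trial is unknown. Under assumed courses the effect lies mainly in the upper quartile and maximum for long, mild, fluctuating symptoms, and is negligible for short episodes with a clear peak. Those figures show direction and possible size only.

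No primary or secondary endpoint, sample size or error rate is affected. The correction is worth making because it costs little and the daily scores are already collected.

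**What to change.** In SAP 5.7.3:

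1. Define duration of maximum severity as the number of days in the episode on which the participant's maximum score for that symptom was recorded.
2. State whether days imputed as 10 (too ill or hospitalized) count towards the maximum and its duration.
3. State that un-imputed missed days are not counted, and report how many there are.
4. If the first-to-last span is kept, present it as time from first to last report of the maximum.
5. Label symptom duration as first to last report. The number of days with the symptom present may be shown beside it.

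The cost is a few sentences in the SAP, matching DPS text and a small change to the derivation. No new data are needed. The downside is that the count may be slightly low where days were missed for other reasons, and item 3 makes this visible.
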